2.3 PRIMARY ENDPOINT MEASURES

- 1) To evaluate and compare pathogen identification of children with musculoskeletal infections using Karius Test NGS and standard culture methods:
 - a. Describe pathogen identification by Karius Test vs. standard culture methods
- 2) To examine the kinetics of pathogen cell-free DNA (cfDNA) in the plasma of children with MSKI and compare the quantity of cfDNA to clinical symptoms and inflammatory markers, CRP, ESR, and procalcitonin (PCT), a biomarker thought to be more specific for bacterial infections.

	Clinical Study Protocol
Title: Plasma-Based Next-Generation Sequencing for Pathogen Detection and Quantification in Children with Musculoskeletal Infections	
Supersedes: 0.8	Document Number: KDG-002 Clinicaltrials.gov #: NCT03846804
	Effective Date: 19Oct2021 Page: 11 of 30

- a. Determine quantification of cf DNA in molecules per microliter (MPM) at each time point using the Karius Test.
- b. Determine CRP, ESR, PCT at each timepoint and compare to cfDNA MPM.

3) To evaluate whether initial detection sample quantitative cfDNA predicts severe disease in children with MSKI.

- a. Determine the correlation of cfDNA level in MPM to severity of infection (defined in SECTION 2.1)

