3 STUDY DESIGN

This is a prospective study of children 6 months to 18 years of age (inclusive) with the diagnosis of MSKI at Riley Hospital for Children (Indianapolis, IN) over a 12-month period. Eligible subjects will be identified by referral from the infectious diseases and orthopedic services at RHC. Subjects will be identified and screened for eligibility (Section 5.3) by the study team. Subjects and their parent(s) or guardian(s) will be informed of the study and, upon providing informed consent, will be enrolled in the study.

Study samples will be collected to coincide with routine clinical care. Samples will be collected when sufficient sample is available after routine care samples are obtained. Additional venipunctures specific for collection of study samples will be performed only with participant's consent.

Collection of NGS samples for real-time testing:

Detection samples will be collected prior to any surgical procedures and will be sent to Karius® Laboratory (Redwood City, CA) for real-time testing to determine if the pathogen is detected by NGS. Karius will notify the study team of the result(s). A positive result for any detection sample will qualify the collection of subsequent study samples. Detection samples will be collected within 96 hours of enrollment, and if applicable, 12-72 hours after the first sample, upon any re-admission for MSKI, or when prior detection sample results are inconclusive.

Collection of subsequent study samples

If NGS testing identifies a pathogen in the detection sample(s), subsequent study samples will, will be collected \geq 48 hours after previous sample collected. When the Detection NGS result(s)

Clinical Study Protocol	
Title: Plasma-Based Next-Generation Sequencing for Pathogen Detection and Quantification in Children with Musculoskeletal Infections	
Supersedes: 0.8	Document Number: KDG-002 Clinicaltrials.gov #: NCT03846804
	Effective Date: 19Oct2021
	Page: 12 of 30

is inconclusive or still pending, study samples may be collected at the appropriate timepoint(s). Collected sample(s) will be sent to Karius with qualifying result(s) from the Detection NGS sample(s). Up to 4 samples, including detection samples, will be collected per inpatient admission. (**Figure 1**)

[figure not shown]

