Figure 1. Study Design- Samples for NGS testing will be collected to coincide with routine clinical care testing. Detection sample(s) sent for real-time NGS testing to determine if the Karius test identifies a pathogen. If a pathogen is detected by NGS, additional study samples will be collected throughout the treatment and follow up for MSKI.

Collection of Synovial Fluid from patients with septic arthritis:

When synovial fluid is obtained as part of routine medical care, excess or leftover synovial fluid may be collected and sent to Karius for potential NGS testing of the synovial fluid.

Procalcitonin:

A procalcitonin (PCT) level will be obtained at each study sample time point, along with routine clinical labs when sufficient sample can be collected.

If the Karius Test identifies an infectious agent in a clinically meaningful timeframe that may be of interest for the treating physician, [name], at his discretion, can contact the attending

Clinical Study Protocol	
Title: Plasma-Based Next-Generation Sequencing for Pathogen Detection and Quantification in Children with Musculoskeletal Infections	
Supersedes: 0.8	Document Number: KDG-002 Clinicaltrials.gov #: NCT03846804
	Effective Date: 19Oct2021

physician and notify them. [name] will stress that these results are from a research-use only test but will guide the treating physician to confirm the diagnosis with a commercially available CLIA-approved test.

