4 STUDY METHODS

Plasma samples will be obtained at the time points outlined in **Section 3**. Approx 2-4ml of whole blood will be collected in 2mL K2-EDTA tubes for NGS testing and centrifuged at 1,600 RCF for 10 minutes at room temperature, within 24 hours of blood draw. Plasma will be transferred into sterile polypropylene tubes. Detection samples will be sent at ambient temperature to Karius Laboratory within 96 hours of blood draw. Subsequent NGS samples will be frozen at -20°C until shipping to Karius. For patients with septic arthritis, in which synovial fluid is collected as part of standard of care, left-over synovial fluid will be frozen at -20°C until shipping to Karius. Blood and source specimen (bone biopsy, abscess aspiration, or synovial fluid) cultures for standard microbiologic diagnosis, will be collected as per the treating physicians. Cultures will be performed per standard of care procedures by the Indiana University clinical laboratory. Standard of care laboratory testing (e.g., ESR, CRP) will be obtained per the treating physicians and run in the Indiana University (IU) clinical laboratory. Additionally, procalcitonin (PCT), which is not part of current standard of care laboratory testing, will be drawn with NGS samples and run in the IU clinical laboratory for research purposes only.

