10 STATISTICAL CONSIDERATIONS

10.1 General Conditions for Statistical Analysis

Positive and negative agreement (percentage) will be used to compare culture and NGS for pathogen identification. Correlation between inflammatory markers and cfDNA quantification will be compared using Spearman's coefficient. Lastly, simple regression modeling will be used to assess the ability of cfDNA to predict severe disease.

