Culture Pathogen ID	Name of pathogen by culture
Culture source	Blood, bone/synovial fluid/tissue, both
NGS Pathogen ID- (IP1)	Name of pathogen by NGS
NGS Quantification- (IP1)	Molecule per microliter (MPM) of cfDNA
NGS Pathogen ID- (IP2)	Name of pathogen by NGS
NGS Quantification- (IP2)	Molecule per microliter (MPM) of cfDNA
NGS Pathogen ID- (IP3)	Name of pathogen by NGS
NGS Quantification- (IP3)	Molecule per microliter (MPM) of cfDNA
NGS Pathogen ID- (IP4)	Name of pathogen by NGS
NGS Quantification- (IP4)	Molecule per microliter (MPM) of cfDNA
NGS Pathogen ID- (OP1)	Name of pathogen by NGS
NGS Quantification- (OP1)	

	Clinical Study Protocol
	Title: Plasma-Based Next-Generation Sequencing for Pathogen Detection and Quantification in Children with Musculoskeletal Infections
Supersedes: 0.8	Document Number: KDG-002 Clinicaltrials.gov #: NCT03846804
	Effective Date: 19Oct2021

	Molecule per microliter (MPM) of cfDNA
NGS Pathogen ID- (OP2)	Name of pathogen by NGS
NGS Quantification- (OP2)	Molecule per microliter (MPM) of cfDNA
NGS Pathogen ID- (OP3)	Name of pathogen by NGS
NGS Quantification- (OP3)	Molecule per microliter (MPM) of cfDNA
WBC x 10 ³ /uL	White blood cell count
WBC Timepoint	(MM-DD-YYYY); 00:00
CRP	mg/dL
CRP Timepoint	(MM-DD-YYYY); 00:00
ESR	mm/hr
ESR Timepoint	(MM-DD-YYYY); 00:00
PCT	ng/mL
PCT Timepoint	(MM-DD-YYYY); 00:00

Clinical Study Protocol	
Title: Plasma-Based Next-Generation Sequencing for Pathogen Detection and Quantification in Children with Musculoskeletal Infections	
Supersedes: 0.8	Document Number: KDG-002 Clinicaltrials.gov #: NCT03846804
	Effective Date: 19Oct2021 Page: 29 of 30

Clinical Study Protocol	
Title: Plasma-Based Next-Generation Sequencing for Pathogen Detection and Quantification in Children with Musculoskeletal Infections	
Supersedes: 0.8	Document Number: KDG-002 Clinicaltrials.gov #: NCT03846804
	Effective Date: 19Oct2021
Page: 30 of 30	

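### Positive NGS results can prompt confirmatory tests, and the plan neither keeps those tests out of the culture comparator nor records culture times; if counted, they would shift the agreement figures

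*Combined protocol and SAP*

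**What the plan says.** Section 3 (Study Design) sets the trigger: "If the Karius Test identifies an infectious agent in a clinically meaningful timeframe that may be of interest for the treating physician", the study physician, "at his discretion, can contact the attending" physician. He stresses that the test is for research use only, and he "will guide the treating physician to confirm the diagnosis with a commercially available CLIA-approved test". No matching step is given for a negative result.

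The same section has NGS run in real time and fixes the order of sampling: "Detection samples will be collected prior to any surgical procedures". Operative source cultures therefore come after the index sample.

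The comparator is culture. The first primary endpoint in Section 2.3 is "Describe pathogen identification by Karius Test vs. standard culture methods", and the only analysis for it, in Section 10.1, is "Positive and negative agreement (percentage) will be used to compare culture and NGS for pathogen identification". Section 4 says that blood and source specimen "cultures for standard microbiologic diagnosis, will be collected as per the treating physicians". These sections give no window, no cut-off at communication and no blinding of culture decisions to NGS.

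Section 10.2 lists a date and time for the NGS sample, the initial antibiotic, WBC, CRP, ESR and PCT. For culture it lists only pathogen and source. The form in Appendix C likewise has one entry, "Name of pathogen by culture", and a source. It has no culture time, no communication time and no place for a non-culture confirmatory result. Section 9.2 (Adjudication Process) is marked not applicable.

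**The concern.** An agreement study needs its comparator to be obtained without regard to the index test. Here a positive index result can itself lead to further testing, and a negative one cannot do so by the same route. If the further test is a culture that grows the NGS organism, a discordant child becomes concordant because the NGS result was known.

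Both halves of hypothesis 1 in Section 2.1 are exposed: high positive agreement in culture-positive infections, and added detection in culture-negative ones. With no culture time and no communication time in the planned data, prompted cultures could not be separated from independent ones, so a sensitivity analysis could not be run from that data set.

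**Working it through.** **The plan's own figure.** Section 10.4 gives at least 50 admissions and participation above 75%: 50 × 0.75 = 37.5, rounded up to 38. This reproduces the target of 38. It is a feasibility count. The documents give no expected agreement, margin or precision to reproduce.

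**Inputs.**
- N = 38 (Section 10.4).
- Culture split 19 positive and 19 negative. This is assumed; Section 1.1 says nearly half of these infections stay culture-negative.
- NGS-positive in 17 of 19 culture-positives and in 8 of 19 culture-negatives. Both are assumed; the documents give no such counts.

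**Formulas.** Let a = NGS+/culture+, b = NGS+/culture−, c = NGS−/culture+, d = NGS−/culture−.
- Positive agreement = a/(a+c).
- Negative agreement = d/(b+d).
- NGS detection among culture-negatives = b/(b+d) = 1 − negative agreement.

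If k children convert through prompted cultures, a becomes a+k and b becomes b−k. Then (a+k)/(a+k+c) exceeds a/(a+c) whenever c > 0, and d/(b−k+d) exceeds d/(b+d) whenever d > 0. Both agreements rise, and detection among culture-negatives falls by exactly the gain in negative agreement.

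**Main illustration (a=17, b=8, c=2, d=11).**

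| k | Positive agreement | Negative agreement | NGS detection in culture-negatives |
|---|---|---|---|
| 0 | 17/19 = 89.5% | 11/19 = 57.9% | 8/19 = 42.1% |
| 1 | 18/20 = 90.0% | 11/18 = 61.1% | 7/18 = 38.9% |
| 3 | 20/22 = 90.9% | 11/16 = 68.75% | 5/16 = 31.25% |
| 5 | 22/24 = 91.7% | 11/14 = 78.6% | 3/14 = 21.4% |

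The k = 0 row is also the result if the prompted test is not a culture and is not counted.

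**Other assumed tables.** With a=15, b=10, c=4, d=9, moving from k = 0 to k = 1 and k = 5 takes positive agreement from 15/19 = 78.9% to 16/20 = 80.0% and 20/24 = 83.3%. Negative agreement goes from 9/19 = 47.4% to 9/18 = 50.0% and 9/14 = 64.3%. Over a = 14 to 17 and b = 6 to 13, with 19 children in each culture group, k = 3 adds 1.4 to 3.6 points to positive agreement and 5.9 to 12.8 points to negative agreement.

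**Does one-sidedness matter?** Take a=15, b=10, c=4, d=9 again and suppose that further cultures convert 30% of the culture-negatives tested.
- NGS-positives only: positive agreement 18/22 = 81.8%, negative agreement 9/16 = 56.25%.
- NGS-negatives as well, at the same yield: c = 4 + 0.3 × 9 = 6.7 and d = 6.3. Positive agreement is 18/24.7 = 72.9% and negative agreement 6.3/13.3 = 47.4%.

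The upward shift in both measures comes from testing one side only.

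**The case against.** The strongest reply is that Section 3 points the physician to any commercial CLIA-approved test, while Sections 2.3 and 10.1 compare NGS with culture. On a plain reading a non-culture confirmatory test never enters the table. This stands as far as it goes: the effect is conditional. But no rule says that such a test is left out, and nothing keeps out a prompted culture.

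Second, a reader might infer that only NGS-positive children can receive further reference testing. The documents do not support that. Section 4 leaves cultures in every child to the treating physicians, so an NGS-negative child can have later cultures too. Only the communication trigger is one-sided, and it is further limited to one physician's discretion and a clinically meaningful timeframe.

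Third, a reader might infer that the bias simply favours the test. It does not. The gain in negative agreement is the complement of a loss in added detection, which is the other half of hypothesis 1. Positive agreement moves by at most 2.2 points in the main illustration, against an exact 95% interval for 17/19 of about 67% to 99%. Five conversions would mean 5 of 8 NGS-only children later growing the organism. No document supports that yield, and Section 1.1 names prior antibiotics as a cause of negative culture.

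Fourth, cutting the comparator at communication would bring its own bias. It would shorten the culture record only in notified NGS-positive children, and it could discard routine operative cultures. This stands, and it shapes the fix.

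Finally, the log linking subject IDs to medical records (Section 10.2) might let culture times be recovered. That is possible, but it is not planned, and communication times would still be missing. The content of Appendix A (Schedule of Events) was not in the text available for this check, so it should be looked at for any culture window.

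**Conclusion.** The point holds as a gap in the plan with a conditional effect. The protocol allows confirmatory testing triggered by a positive NGS result, does not exclude its result from the comparator, and does not plan to record the times needed to separate it. It would be too strong to say that the design raises agreement: that requires the prompted test to be a culture, or to be counted as one, and to be positive for the same organism.

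Where that happens, positive agreement rises slightly. Negative agreement rises more, by about 3 to 21 points for 1 to 5 conversions in the main illustration (57.9% to 61.1% and 78.6%), and NGS detection among culture-negatives falls by the same amount. These sizes rest on assumed cell counts and an assumed even culture split. The direction does not, provided c and d are above zero. With about 19 culture-negative children, a handful of conversions would visibly change what is reported for objective 1.

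**What to change.** Leave the disclosure rule as it is.

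1. In Section 10.1, define the comparator as cultures from specimens collected within one fixed window around the first detection sample, the same for every child whatever the NGS result. The study team should set its length before the comparison is made, with routine operative cultures in mind.
2. State that non-culture confirmatory tests do not count in the comparator. Tabulate them, and cultures outside the window, separately.
3. Report positive and negative agreement with and without cultures collected after an NGS result was communicated. This is needed because a prompted culture can still fall inside the window. The version without them is a sensitivity analysis, since it shortens the record only in notified children.
4. Add to the Section 10.2 data set and the Appendix C form the collection date and time of each culture, and the date and time of any communication. Check also that the form captures the detection sample time: Section 10.2 lists it, but the form as printed shows no field for it.

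The cost is a few form fields, one extra table, and some late true culture positives moved to the secondary table.

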4 STUDY METHODS

Plasma samples will be obtained at the time points outlined in **Section 3**. Approx 2-4ml of whole blood will be collected in 2mL K2-EDTA tubes for NGS testing and centrifuged at 1,600 RCF for 10 minutes at room temperature, within 24 hours of blood draw. Plasma will be transferred into sterile polypropylene tubes. Detection samples will be sent at ambient temperature to Karius Laboratory within 96 hours of blood draw. Subsequent NGS samples will be frozen at -20°C until shipping to Karius. For patients with septic arthritis, in which synovial fluid is collected as part of standard of care, left-over synovial fluid will be frozen at -20°C until shipping to Karius. Blood and source specimen (bone biopsy, abscess aspiration, or synovial fluid) cultures for standard microbiologic diagnosis, will be collected as per the treating physicians. Cultures will be performed per standard of care procedures by the Indiana University clinical laboratory. Standard of care laboratory testing (e.g., ESR, CRP) will be obtained per the treating physicians and run in the Indiana University (IU) clinical laboratory. Additionally, procalcitonin (PCT), which is not part of current standard of care laboratory testing, will be drawn with NGS samples and run in the IU clinical laboratory for research purposes only.

5 SELECTION AND WITHDRAWAL OF SUBJECTS

5.1 Study Population

We will prospectively enroll children, 6 months to 18 years of age, evaluated at Riley Hospital for Children (RHC) with clinical presentation consistent with a musculoskeletal infection (osteomyelitis, septic arthritis, or pyomyositis; MSKI) over a 12-24-month period. Eligible subjects will be identified by referral from the infectious diseases and orthopedic services at RHC.

5.2 Medications

There are no medication restrictions or medication requirements for this study.

	Clinical Study Protocol Title: Plasma-Based Next-Generation Sequencing for Pathogen Detection and Quantification in Children with Musculoskeletal Infections	
Supersedes: 0.8	Document Number: KDG-002 Clinicaltrials.gov #: NCT03846804	
	Effective Date: 19Oct2021	Page: 14 of 30

5.3 Inclusion Criteria

Eligible subjects will be identified by referral from the infectious diseases and orthopedic services at RHC. Subjects and their parent(s) or guardian(s) will be informed of the study and, upon providing informed consent, will be enrolled in the study if they meet the following inclusion criteria:

1. 6 months (to ensure adequate blood volume drawn) to 18 years of age.
2. Strong clinical suspicion of MSKI as evidenced by fever, osteoarticular pain (e.g. tenderness to palpation of a joint, bone pain, or refusal to bear weight); and elevated ESR or CRP.

5.4 Exclusion Criteria

1. Subjects will be excluded if they have clinical evidence suggesting an alternative diagnosis; PI discretion; inability or unwillingness to consent for the study.
2. Subjects will be excluded if they have a surgical procedure prior to obtaining NGS samples.

5.5 Subject Screening and Enrollment

The study team will be notified by the pediatric infectious diseases and/or orthopedic team, at admission/evaluation, of any child presenting with possible MSKI. A study team member will screen the patient for eligibility (**Section 5.3**), and if eligible will obtain informed consent/assent for study participation.

5.6 Subject Withdrawal

5.6.1 Withdrawal Criteria

The primary consideration in any determination to discontinue a subject's participation must be the health and welfare of the subject. Reasons for study withdrawal may include but are not limited to:

- a) A serious medical complication or an unacceptable situation, whether attributed to study procedure or not.
- b) Noncompliance with study procedures.
- c) Subject's right to withdraw their consent at any time during the study with or without stated reason.
- d) The PI's opinion is that it is not in the subject's best interest to continue study participation.

5.6.2 Documentation of Withdrawal of Subjects

	Clinical Study Protocol
	Title: Plasma-Based Next-Generation Sequencing for Pathogen Detection and Quantification in Children with Musculoskeletal Infections
Supersedes: 0.8	Document Number: KDG-002 Clinicaltrials.gov #: NCT03846804
	Effective Date: 19Oct2021

Document the reasons for early withdrawal of any subject from the study on the appropriate Case Report Forms (CRF). If the reason for early withdrawal is an adverse event or an abnormal laboratory value, record the specific event or test result on the relevant CRF.

5.7 Study Termination

Sponsor has the right to terminate this study at any time. Reasons for terminating the study may include, but are not limited to, the following:

- a) Subject enrollment is unsatisfactory.
- b) Data recording is inaccurate or incomplete.
- c) Investigators do not adhere to the protocol or applicable regulatory guidelines in conducting the study.

6 TREATMENT OF SUBJECTS

6.1 Treatment Regimen(s)

NA

7 STUDY PROCEDURES

7.1 Screening

Patients will be screened for eligibility (**Section 5.3**) by the study team at evaluation at RHC.

7.2 Study Visits

Study visits coincide with a patient's course of treatment for MSKI by Riley Pediatric Infectious Disease at RHC. Up to 4 visits may occur per inpatient admission and up to 4 visits may occur per outpatient course.

7.3 Sample Handling

Sample collection materials may be supplied by the sponsor. The main sample handling instructions are as below:

All samples should be collected using the institutional guidelines for sterile sample collection. The venous blood sample collection can be collected from either a peripheral vein or a central line catheter.

A) Detection Samples:

	Clinical Study Protocol	
	Title: Plasma-Based Next-Generation Sequencing for Pathogen Detection and Quantification in Children with Musculoskeletal Infections	
Supersedes: 0.8	Document Number: KDG-002 Clinicaltrials.gov #: NCT03846804	
	Effective Date: 19Oct2021	Page: 16 of 30

Specimen: Minimum 1.2 mL of plasma isolated from whole blood collected in K2-EDTA tube within 24 hours of draw by centrifugation of the specimen at 1,600 RCF for 10 minutes and transferred to a sterile polypropylene tube. Ship to Karius laboratory at ambient temperature. Must be received within 96 hours (4 days) of collection.

B) Subsequent study samples:

- B1. Collect 2-4.0 mL of whole blood in a K2-EDTA 2.0 mL blood collection tube
- B2. CRITICAL STEP: Immediately after collection, gently invert the filled tube 180° and back 8-10 times to adequately mix the blood and tube reagents together.
- B3. Place tube upright in rack at room temperature. The tube may be stored upright at room temperature for no more than 24 hours prior to processing for plasma collection. Do not freeze or refrigerate the tube.
- B4. For plasma collection, centrifuge the K2-EDTA blood tube at 1,600 rcf for 10 minutes at 20°C. It is critical that tubes be centrifuged at the appropriate speed to ensure proper plasma separation.
- B5. Using a sterile micropipette, transfer blood plasma (top layer) into labeled 1.0 mL aliquot tubes. Take care not to disturb the pellet at the bottom of the tube by tilting the tube and placing the pipette tip along the lower side of the collection tube wall.
- B6. In order to ensure Karius receives sufficient sample for processing and to avoid tubes cracking prior to shipment, each aliquot tube should ideally be filled to 1.0 mL with plasma after processing. If there is plasma that won't fill a full tube, the remaining amount should still be sent to Karius.
- B7. Freeze the plasma samples immediately following processing by transferring to 80°C freezer. Store all samples in -80°C until transport to Karius.

